#### 9.1 Adverse Events

All adverse events (AEs) will be coded by system organ class (SOC) and Medical Dictionary for Regulatory Activities (MedDRA) Preferred Term (PT). The incidence of the following events in the treatment period and the extension period will be summarized by treatment group and overall:

a) Treatment-emergent AEs (TEAEs)

- b) TEAEs by severity
- c) TEAEs potentially causally related to the digital therapeutic (CT-152 or sham)
- d) TEAEs with an outcome of death
- e) Serious TEAEs
- f) TEAEs leading to discontinuation of the digital therapeutic (CT-152 or sham)

Deaths, SAEs, and AEs leading to discontinuation from digital therapeutic or trial, will be listed by subject on the Safety Sample.

#### 9.1.1 Adverse Events in the Treatment Period

TEAEs in the treatment period are defined as AEs with an onset date on or after the start of double-blind digital therapeutic. In more detail, TEAEs are all adverse events which started after the first use of double-blind digital therapeutic; or if the event was continuous from baseline and was worsening, serious, study digital therapeutic related, or resulted in death, discontinuation, interruption or reduction of study digital therapeutic. Adverse Events prior to the start of the extension period will be included in the summary tables.

The incidence of AEs in the treatment period will be tabulated by treatment group and overall on the Safety Sample. Incidence of TEAE during the treatment period of at least 5% in CT-152 group and also greater than sham by SOC and MedDRA PT will be provided.

#### 9.1.2 Adverse Events in the Extension Period

TEAEs in the extension period are defined as AEs with an onset date during that period, or if the event was continuous from the treatment period and was worsening, serious, study digital therapeutic related, or resulted in death or discontinuation. AEs occurring through the last subject visit or contact in this period will be included in these summary tables.

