^jAdverse events will be collected from the signing of the informed consent document through the last subject visit or contact. Serious adverse events will be collected from the signing of the informed consent through and including 28 calendar days after the last use of CT-152 or sham.

^kSubject debriefing will occur at the conclusion of a subject's participation in the trial and after all final visit procedures have been completed.

Protocol No. 345-201-00002

2 Introduction

CT-152 is a prescription digital therapeutic intended for the treatment of major depressive disorder (MDD) in adults. It is intended for use as an adjunct to standard of care (pharmacotherapy) and under the supervision of a clinician. The current trial is designed to provide data regarding effectiveness and safety for CT-152.

CT-152 is being co-developed by Otsuka Pharmaceutical Development & Commercialization, Inc. and Click Therapeutics, Inc.

This trial will evaluate the effectiveness of CT-152 in reducing depressive symptoms in adult subjects diagnosed with MDD who are on antidepressant therapy (ADT) monotherapy. CT-152 delivers an interactive, software-based intervention featuring cognitive-emotional training, psychotherapy lessons, psychotherapy messages, and engagement messages. CT-152 will be evaluated relative to a sham arm which will serve as a control that deploys only a working memory exercise. In order to retain the placebo nature of the sham, it will not include psychotherapy content.

Abbreviations used are listed in Section 10.5.

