Unanticipated adverse device effect: Any serious adverse effect on health or safety or any life-threatening problem or death caused by, or associated with, a device, if that effect, problem, or death was not previously identified in nature, severity, or degree of incidence in the investigational plan, or any other unanticipated serious problem associated with a device that relates to the rights, safety, or welfare of subjects.

Nonserious AEs: All AEs that do not meet the criteria for a "serious" AE.

Severity: Adverse events will be graded on a 3-point scale and reported as indicated in the eSource. The severity of an adverse experience is defined as follows:

1 = Mild: Discomfort noticed, but no disruption to daily activity.

2 = Moderate: Discomfort sufficient to reduce or affect normal daily activity.

3 = Severe: Inability to work or perform normal daily activity.

Causality: Assessment of causal relationship of an AE to the use of CT-152 is defined as follows:

Related: There is a reasonable possibility of a temporal and causal

relationship between CT-152 and the AE.

Not Related: There is no temporal or causal relationship between CT-152 and

the AE.

Additional definitions (based on Otsuka internal procedures):

63

Protocol No. 345-201-00002

Treatment-emergent AEs (TEAEs): TEAEs are defined as an AE that began after at least one occurrence of CT-152 or sham; or if the event was continuous from baseline and was worsening, serious, related, or resulted in death, discontinuation, or interruption of investigational product.

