8.3.4.2 Follow-up of Immediately Reportable Events

This trial requires that subjects be actively monitored for IREs up to 28 calendar days after the last subject visit or contact.

Immediately reportable events that are **identified or ongoing at the last scheduled contact** must be recorded as such on the AE eSource and the IRE form. If updated information (eg, resolved status) on IRE status becomes available after a subject's last scheduled contact (up to the last remote visit or telephone contact for the entire trial), this

Protocol No. 345-201-00002

must be reported to the sponsor and recorded in the AE eSource and the IRE form, according to the appropriate reporting procedures described in Section 8.3.2.4.

It is expected that the investigator will provide or arrange appropriate supportive care for the subject and will provide prompt updates on the subject's status to the sponsor. The investigator will follow IREs until the events are:

- resolved.
- stabilized,
- the subject is lost to follow-up, or
- has died.

[figure not shown]
Resolution means that the subject has returned to the baseline state of health and stabilized means that the investigator does not expect any further improvement or worsening of the subject's condition. The investigator will continue to report any significant follow-up information to the sponsor up to the point the event has resolved or stabilized, or the subject is lost to follow-up, or has died.

Refer to Section 10.3 for additional information regarding the follow-up period for subjects that become pregnant.

8.3.4.3 Follow-up and Reporting of Immediately Reportable Events Occurring After Last Scheduled Contact

Any new IREs reported to the investigator which occur after the last scheduled contact and are determined by the investigator to be reasonably associated with the use of CT-152 or sham, should be reported to the sponsor according to the procedures outlined in Section 8.3.2.4. This may include IREs that are captured on follow-up telephone contact or at any other time point after the defined trial period and continue to report any significant follow-up information to the sponsor until the events are resolved or stabilized, or the subject is lost to follow-up or has died.

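### SAEs starting after the last extension-period contact reach a listing but no by-arm incidence; two unreconciled protocol windows make the gap 0 to 28 days for a typical completer

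*SAP*

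**What the plan says.** SAP 9.1 defines the by-arm incidence tables, which include related, fatal and serious TEAEs, for two periods: "The incidence of the following events in the treatment period and the extension period will be summarized by treatment group and overall". Section 9.1.1 fills the first: "Adverse Events prior to the start of the extension period will be included in the summary tables". Section 9.1.2 ends the second: "AEs occurring through the last subject visit or contact in this period will be included in these summary tables". No follow-up table is planned, and the SAP addendum does not touch these sections. SAP 9.1 also has a listing with no stated end date: "Deaths, SAEs, and AEs leading to discontinuation from digital therapeutic or trial, will be listed by subject on the Safety Sample".

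The protocol collects SAEs for longer than other events, but gives two end points. Table 1.3-1 footnote j collects them "through and including 28 calendar days after the last use of CT-152 or sham". Section 8.3.4.2 counts from a different date: "This trial requires that subjects be actively monitored for IREs up to 28 calendar days after the last subject visit or contact". IREs include every SAE (Section 8.3.2.4). Section 8.3.4.3 then asks for new IREs after the last scheduled contact to be reported when they are "determined by the investigator to be reasonably associated with the use of CT-152 or sham".

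The protocol's TEAE definition has a start but no end: "TEAEs are defined as an AE that began after at least one occurrence of CT-152 or sham". Protocol 9.4.2.1 promises serious, fatal and related TEAE incidence by treatment group without a cut-off.

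**The concern.** The SAP applies the end date for ordinary adverse events to serious ones as well. For a subject in the extension, an SAE recorded after the last contact falls after both tables close. Reading contact broadly does not help: SAP 9.1.2 limits it to contact within the extension, which is Weeks 7 to 10, so a later follow-up call lies outside.

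No other summary fills the gap. The C-SSRS is last given at Week 10, SAP 9.3 summarizes the same two periods, and SAP 9.4 compares worsening depression in the treatment period only.

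The protocol names worsening depression and suicidal ideation as examples of serious events (Section 8.3.1), and these can arise after visits stop. With few SAEs expected, one or two uncounted events could alter the by-arm comparison, and the listing could show more SAEs than the tables.

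**Working it through.** The plan states no figure on this point, so there is none to reproduce. The check is day arithmetic, followed by a size estimate under an assumed SAE rate.

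**Inputs.** Scheduled sessions end at Week 6, Day 42 (Protocol 6.1.1). The last visit is Day 70, with a window of ±3 days (Table 1.3-1). Both SAE windows last 28 days. The SAP cut-off is the last visit or contact in the extension.

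**Days collected but not tabulated.**
- Footnote j: (last use + 28) − last contact; zero or negative means no gap.
- Section 8.3.4.2: (last contact + 28) − last contact = 28.

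| Subject who entered the extension | Footnote j | Section 8.3.4.2 |
|---|---|---|
| Last use Day 42, last visit Day 70 | 42 + 28 − 70 = 0 | 28 |
| Last use Day 42, last visit Day 67 | 70 − 67 = 3 | 28 |
| Last use Day 42, last visit Day 73 | 70 − 73 = −3 (no gap) | 28 |
| Last use Day 42, leaves on Day 50 | 70 − 50 = 20 | 28 |
| Last use Day 70, last visit Day 70 | 70 + 28 − 70 = 28 | 28 |

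Under Section 8.3.4.2 a Day 70 completer is followed to Day 98, so the untabulated share is 28/98 = 28.6%.

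The last row matters for comparability. After Week 6 the memory tasks are withdrawn in both arms, but earlier psychotherapy content stays open for optional reference in the CT-152 arm only (Protocol 6.1.1). The protocol does not define last use. If opening that content counts, footnote j can give CT-152 subjects a longer SAE window than sham subjects.

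**Size.** The documents give no SAE rate. Assume a proportion r of subjects has an SAE over 70 days, with constant hazard h = −ln(1 − r)/70 and complete ascertainment to Day 98. Expected first SAEs per arm in the extra 28 days are N × [exp(−70h) − exp(−98h)] = N × [(1 − r) − (1 − r)^1.4].

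| r over 70 days | N = 180 per arm | N = 270 per arm |
|---|---|---|
| 0.5% | 0.36 | 0.54 |
| 1% | 0.71 | 1.07 |
| 2% | 1.42 | 2.13 |
| 4% | 2.80 | 4.20 |

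These are ceilings. No visit or call is scheduled after Day 70, and Section 8.3.4.3 directs reporting only of associated new events, so unrelated late SAEs may never be recorded.

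**Which events are affected.** Nonserious AEs are collected only through the last visit or contact (Protocol 8.3.2), so the SAP cut-off loses none of them, and the related-TEAE table can lose only serious related events. An event with onset before the cut-off that later proves fatal still belongs in the tables. For subjects who stop before Week 6 and never enter the extension, SAP 9.1.1 gives no end date, so their late SAEs are neither clearly in nor clearly out.

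**The case against.** The case for leaving the SAP alone has four parts.

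- The cut-off matches the protocol's general AE collection rule. This holds for nonserious events. Footnote j, however, sets a separate and later end for SAEs, which the SAP does not follow. That Protocol 9.4.2.1 would count later events is an inference from an open-ended TEAE definition, not an explicit contradiction.
- Under footnote j a completer's window closes at about Day 70, so nothing is lost. This is correct for last use on Day 42 and a Day 70 visit. It does not cover early leavers, late optional use or the Section 8.3.4.2 window.
- Subjects are debriefed at the end of participation, so later reports and causality judgements follow disclosure of the hypothesis and could be biased. This is a good reason to show late events separately, but not to omit a by-arm count.
- The listing shows every recorded death and SAE, and numbers will be small. This lowers the stakes, but a listing gives no by-arm incidence.

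A reader might infer that every completer has 28 more days of SAE collection, that about 29% of SAEs are therefore lost, or that late events disappear from every by-arm table and from reporting. The documents do not support this. The 28 days for every completer rests on Section 8.3.4.2 alone, against footnote j. The 29% needs constant hazard and full ascertainment. Events starting before the cut-off are still counted, and late ones are listed.

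**Conclusion.** The gap is real but limited. For subjects who enter the extension, a recorded SAE with onset after the last visit or contact is in no by-arm serious, fatal or serious related TEAE incidence. For a completer with last use on Day 42 and a Day 70 visit, the gap is 0 days under footnote j and 28 of 98 days under Section 8.3.4.2. Someone who leaves the extension on Day 50 has a gap of 20 or 28 days. At 180 per arm the ceiling is about 0.4 to 2.8 first SAEs per arm, assuming 0.5% to 4% of subjects have one over 70 days, constant hazard and full ascertainment. No efficacy result or alpha level depends on this. It is still worth correcting, because so few SAEs are expected and the arms may have unequal windows if last use is the anchor.

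**What to change.** 1. Reconcile Table 1.3-1 footnote j with Sections 8.3.4.2 and 8.3.4.3 of the protocol, and define last use. The choice of window is for the sponsor; the passages need to agree.
2. Whatever window results, state in SAP 9.1.2 that every recorded serious or fatal TEAE, and every serious related TEAE, with onset after first app use is counted by arm. Put events after the last contact in a separate follow-up column, noted as arising after debriefing, and include them in one whole-trial row.
3. Say explicitly that this covers early discontinuers, including those who never enter the extension, since SAP 9.1.1 gives them no end date.
4. Keep the last-contact cut-off for nonserious AEs.

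The SAP cost is a short text change, a date filter and one extra column, using events already recorded. Reported SAE incidence may be slightly higher.

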#### 9.2 Clinical Laboratory Tests

Listings of urine drugs-of-abuse screen and pregnancy test results by subject will be provided.

# 9.3 Suicidality Data

Suicidality will be monitored during the study using the C-SSRS and will be summarized as number and percentage of subjects reporting any suicidal behavior, ideation, behavior by type (4 types), ideation by type (5 types) and treatment emergent suicidal behavior and ideation. Summary will be provided for the treatment period and extension period on the Safety Sample.

Suicidality is defined as report of at least one occurrence of any type of suicidal ideation or at least one occurrence of any type of suicidal behavior during assessment period (count each person only once).

Treatment emergent suicidal behavior and ideation is summarized by four types: Emergence of suicidal ideation, Emergence of suicidal ideation, Worsening of suicidal ideation, Emergence of suicidal behavior.

Emergence of suicidal behavior/ideation is defined as report of any type of suicidal behavior/ideation during treatment when there was no baseline suicidal behavior/ideation.

Emergence of serious suicidal ideation is defined as observation of suicidal ideation severity rating of 4 or 5 during treatment when there was no baseline suicidal ideation.

Worsening of suicidal ideation is defined as a suicidal ideation severity rating that is more severe than it was at baseline.

## 9.3.1 Clinically important suicidality

Clinically important suicidality may include:

- 1) Suicidal behavior (with or without intent of suicide or serious self-harm)
- 2) Acute suicidality to such a degree that precaution against suicide must be exercised.
- Response of "yes" to C-SSRS ideation items 4 or 5 or any of the C-SSRS behavioral items.
- 4) Score of "4", "5", or "6" on the MADRS suicidal thoughts item.
- 1) and 2) are referred to suicidality-related AEs, which will be identified using Standardized MedDRA Query (SMQ) for suicidality.

The incidence of emergent clinically important suicidality will be compared between CT-152 and sham groups using Cochran-Mantel-Haenszel (CMH) General Association Test on OC dataset. Rates and 95% confidence intervals will be reported and the estimated differences between groups will be provided.

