Trial site staff will implement procedures either by telephone or remote visit via telemedicine technology, at all visits. The screening visit may be performed in person at the discretion of the investigator. A trial site may conduct an unscheduled visit in person or remotely at any time if needed to assess a safety issue/concern.

Remote visits will be conducted using a sponsor-designated telemedicine platform with a portal accessible by the trial site staff, and subjects will be asked to download a mobile application (separate from the investigational digital mobile application) in order to provide consent to the trial and complete trial assessments, including self-administered scales.

Prior to downloading the mobile application for conducting telemedicine visits, subjects will be asked to provide consent to participate in a registry and agree to its privacy policy and terms of service required to collect subjects' information within the telemedicine platform, including identity verification. Subjects will be required to complete the identity verification process remotely before they can electronically sign the trial consent in order to comply with 21 Code of Federal Regulations (CFR) Part 11 electronic signature requirements. Details are found in the Site Operations Manual.

Protocol No. 345-201-00002

The screening period begins after informed consent has been obtained. Subjects who fulfill entry criteria at the screening visit will download the digital mobile application on their smartphone and receive access to an onboarding software module. A call center can assist with the downloading of the digital mobile application. During the screening period, subjects will become familiar with the software. The subject's understanding of, and interest in, the trial will be demonstrated through adequate adherence to onboarding requirements. This will be assessed by the investigator via confirmation with the subject and completion of tasks by the subject CCI during the allotted 3-week screening window.

Following the screening visit, subjects will be considered eligible based upon the following:

- Adherence and performance on the onboarding software module by the subject

 CCI
- Continuing to meet all inclusion and no exclusion criteria based on investigator assessment.

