9.4.2.3 Other Safety Data

Rates of the incidence of worsening depressive symptoms during the treatment period (depressive symptom severity entering the "severe" range: CGI-S increase of 2 or more points from baseline, or as judged by investigator evaluation) and the incidence of emergent clinically important suicidality (as described in Section 8.2.2) will be compared between CT-152 and sham groups in the safety analysis sets. Rates and their 95% confidence intervals will be reported and the estimated differences between groups will be provided.

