#### 5.2 Handling of Missing Data

The MADRS is utilized as the primary efficacy assessment of a subject's level of depression. The MADRS consists of 10 items, all rated on a 0 to 6 scale with zero being the "best" rating and 6 being the "worst" rating. The MADRS total Score is the sum of ratings for all 10 items; therefore, possible total scores range from 0 to 60. The MADRS total Score will be unevaluable if less than 8 of the 10 items are recorded. If 8 or 9 of the 10 items are recorded,

the MADRS total Score will be the mean of the recorded items multiplied by 10 and then rounded to the first decimal place.

The mixed-effect model repeated measure (MMRM) assumes data are missing at random (MAR), which is a reasonable assumption in longitudinal clinical trials in MDD. However, the possibility of "missing not at random" (MNAR) data can never be ruled out. As sensitivity analyses, selection model, pattern-mixture model, and/or shared parameter model will be used to explore data missing mechanisms of MNAR and investigate the response profile of dropout patients by last dropout reason under MNAR mechanism for the following 3 scenarios: 1) Dropout reasons due to either adverse event (AE) or lack of efficacy (LOE) as MNAR, 2) Dropout reasons due to either AE or LOE or subject withdrew consent as MNAR, 3) All dropouts as MNAR using both 1) Delta adjustment imputation method which is to departure from MAR assumption by progressively increasing the delta until conclusion from the primary analysis is overturned, and 2) Placebo based imputation methods in which missing data for both sham and CT-152 group are imputed based on the imputation model derived from sham data. If CT-152 improved outcomes prior to dropout, this benefit is carried into subsequent imputed values, but will diminish over time in accordance with the correlation structure. Details are provided in Section 8.1.3 Sensitivity Analysis.

The observed-cases (OC) data set will consist of actual observations recorded at each scheduled visit during the treatment period and/or extension period and no missing data will be imputed. MMRM, Wu-Bailey, and pattern-mixture model will be performed on the OC dataset.

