# 9.4 Other Safety Analysis

The incidence of worsening depressive symptoms during the treatment period will be compared between CT-152 and sham groups using Cochran-Mantel-Haenszel (CMH) General Association Test on OC dataset. Worsening depressive symptoms are defined as 1) CC 2) Any AE of worsening depression. Rates and

their 95% confidence intervals will be reported and the estimated differences between groups will be provided.

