#### 10 Conventions

## 10.1 Study Visit Windows

Study visit windows will be used to map visits using study day intervals. Observations at each scheduled visit and Early Termination will be assigned to Week 2, Week 4, Week 6, Week 8 and Week 10 based on their visit windows as shown in Table 10.1-1. This visit window convention applies to tables and listings for all efficacy scales (MADRS, GAD-7, CGI-S, PHQ-9, WHODAS2.0, CCI, and CCI). This derived study window variable will be named as WEEK and will be footnoted. In listings it will be listed along with the eCRF study visit.

Table 10.1-1 shows classifications for study day intervals in the treatment period and extension period. The variable "target day" is defined using the number of days since the start of intervention with double-blind digital therapeutic in the treatment period. The first day of intervention with double-blind digital therapeutic is defined as "Day 1". If more than one observation falls within a particular study day interval, then the last observation within that interval is used. Assessments done during the treatment period and occurring more than seven days after the last date of the interaction with double-blind digital therapeutic in the treatment period will be excluded from efficacy analyses of the treatment period.

[figure not shown]
SAP 345-201-00002

Table 10.1-1 Study Day and Visit Windows in the Trial					
Week	Target Day a	Study Day Interval a			
2	14	2~20			
4	28	21~34			
6	42	35~48			
8	56	49-62			
10	70	63-77			

<sup>a Relative to the first day of intervention with double-blind digital therapeutic in the treatment period.

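### Two any-occurrence safety comparisons are run on a scheduled-visit data set, so scale positives from unscheduled visits, or superseded within a window, can go uncounted unless also recorded as adverse events

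*SAP*

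**What the plan says.** Protocol 9.4.2.3 says that the rates of worsening depressive symptoms and of emergent clinically important suicidality "will be compared between CT-152 and sham groups in the safety analysis sets". It mentions neither OC nor scheduled visits.

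SAP 9 makes the Safety Sample the default for safety analyses unless something else is indicated. SAP 9.3.1 then specifies: "The incidence of emergent clinically important suicidality will be compared between CT-152 and sham groups using Cochran-Mantel-Haenszel (CMH) General Association Test on OC dataset". SAP 9.4 says "The incidence of worsening depressive symptoms during the treatment period will be compared between CT-152 and sham groups", again "using Cochran-Mantel-Haenszel (CMH) General Association Test on OC dataset".

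The only definition of OC is in SAP 5.2: "The observed-cases (OC) data set will consist of actual observations recorded at each scheduled visit", in the treatment or extension period, with nothing imputed. SAP 10.1 assigns scheduled and early-termination observations to a week, and adds: "If more than one observation falls within a particular study day interval, then the last observation within that interval is used". It applies this convention to the efficacy scales. MADRS and CGI-S are on that list; C-SSRS and AEs are not.

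Protocol 4.1 provides for extra safety contacts: "A trial site may conduct an unscheduled visit in person or remotely at any time if needed to assess a safety issue/concern".

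The SAP addendum of November 2022 does not change SAP 9.3.1, 9.4, 5.2 or 10.1.

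**The concern.** Both outcomes are of the any-occurrence kind: a subject either had the event in the period or did not. OC is a missing-data construct written for models such as the MMRM, where one value per scheduled visit is what is wanted. Applied to an any-occurrence outcome, it can omit positives picked up between scheduled visits or overwritten inside a visit window. Those are the circumstances in which a deteriorating subject is likely to be seen.

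These are the only two formally tested comparisons of the trial's main psychiatric risks. Lost positives understate incidence. If extra visits or early withdrawals are more frequent in one arm, the arm difference could also be distorted. Even if nothing is lost, the numerator is not fully defined, and two programmers could report different rates from the same data.

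**Working it through.** The documents state no event rate or power for these comparisons, so there is no figure to reproduce. The check sets the rules side by side.

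**1. Which criteria depend on visit scores.**

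| Outcome | Scale-based | AE-based |
|---|---|---|
| Clinically important suicidality (SAP 9.3.1) | C-SSRS ideation items 4 or 5, or any behaviour item; MADRS suicidal-thoughts score of 4 to 6 | Suicidal behaviour and acute suicidality, identified through the suicidality SMQ |
| Worsening depression (SAP 9.4) | Criterion 1 is redacted; Protocol 9.4.2.3 uses a CGI-S rise of at least 2 points or investigator judgment | Any AE of worsening depression |

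Only the scale-based column is directly limited by a scheduled-visit definition. AEs are collected continuously from consent to the last contact (Protocol 8.3.2). The SAP does not say how an AE is attached to a data set made of scheduled-visit observations.

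**2. Unscheduled visits.** A scale score taken at an unscheduled visit is not a scheduled-visit observation, so the SAP 5.2 definition leaves it out. After screening the C-SSRS is given in its Since Last Visit version (Protocol 8.2.2.1). If the unscheduled visit counts as the last visit, the next scheduled C-SSRS need not pick the event up again.

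**3. Displacement within an interval.** The inputs are the SAP Table 10.1-1 intervals and the protocol's ±3-day visit window. Days left after a visit = end of interval − visit day.

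| Week | Allowed visit days | SAP interval | Days left, on-target visit | Days left, across the window |
|---|---|---|---|---|
| 2 | 11–17 | 2–20 | 20 − 14 = 6 | 3 to 9 |
| 4 | 25–31 | 21–34 | 34 − 28 = 6 | 3 to 9 |
| 6 | 39–45 | 35–48 | 48 − 42 = 6 | 3 to 9 |
| 8 | 53–59 | 49–62 | 62 − 56 = 6 | 3 to 9 |
| 10 | 67–73 | 63–77 | 77 − 70 = 7 | 4 to 10 |

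Each interval holds only one in-window scheduled visit, so two on-schedule scores never compete. An earlier MADRS or CGI-S score is replaced only by an early-termination, out-of-window or other extra assessment later in the same interval.

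The protocol makes this possible. Section 8.2.2 allows withdrawal after clinically important suicidality. The schedule of assessments calls for the Day 42 procedures, which include MADRS and CGI-S, as soon as possible after the last use in subjects who stop before Week 6. Example: a subject scores 4 on the MADRS suicidal-thoughts item on Day 14, is withdrawn, and scores 2 at early termination on Day 18. Both days lie in 2–20, so the Day 18 score is kept. The subject is lost to the comparison only if that item was the sole signal, meaning that the C-SSRS was not positive and no AE was recorded.

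**4. The neighbouring summary.** SAP 9.3 summarises C-SSRS on the Safety Sample, by any occurrence in the period, counting each person once. SAP 9.3.1, for a closely related outcome, does not carry that rule over.

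**The case against.** The strongest reply is that the AE criteria are a separate route into both outcomes. A finding at an unscheduled visit that is recorded as an AE can still count, and Protocol 8.3.1 names suicidal ideation and worsening depression as examples of medically significant events. This stands, and it limits the point to scale positives that are not also AEs. The route is not complete, however. Protocol 8.3.2 restricts when exacerbation of the condition is reported as an AE, so a CGI-S rise or a MADRS item score of 4 need not become one.

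It can also be said that OC describes the observations and not the subjects. SAP 8.1.1.2 names the OC data set and the FAS Sample separately, SAP 5.1 mentions FAS-derived data sets for efficacy analyses only, and SAP 9 defaults to the Safety Sample. This stands too. A reader might infer that treated subjects outside the FAS drop out of these comparisons; the documents do not show that.

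Third, C-SSRS and treatment-emergent AEs are also summarised by arm (SAP 9.1 and 9.3), so many signals missed by the tests would remain visible. That is correct, but those summaries are descriptive, and the C-SSRS summary does not include the MADRS item.

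Finally, SAP worsening criterion 1 is redacted, so the CGI-S part rests on the protocol's definition.

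**Conclusion.** The point holds as a defect in a stated rule. SAP 9.3.1 and 9.4 attach a scheduled-visit data set to two any-occurrence safety outcomes. Taken literally, that omits scale positives seen only at unscheduled visits and allows MADRS or CGI-S positives to be superseded within an interval, unless an AE or another criterion counts the subject. Confidence is high on the text and low on the practical effect.

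The size cannot be derived. The documents give no event rates, no frequency of unscheduled visits and no rate at which such findings become AEs, so any percentage would rest on invented inputs. Bias between arms is possible but not shown.

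A reader might go further and conclude that every unscheduled-visit positive is ignored, or that a later C-SSRS overwrites an earlier one. Neither is supported: AEs are separate criteria, and the SAP 10.1 rule does not list C-SSRS. The CGI-S part assumes that the redacted SAP criterion follows Protocol 9.4.2.3.

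**What to change.** In SAP 9.3.1 and 9.4, replace the reference to the OC data set with wording such as: *on the Safety Sample; a subject is counted once if any post-baseline scheduled, unscheduled or early-termination assessment, or any AE, in the period meets the definition; the last-in-window rule of Section 10.1 does not apply.* Keep the CMH test, the rates with their 95% confidence intervals, and the estimated differences.

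This states the protocol's population explicitly and matches the counting rule already used in SAP 9.3. It costs one sentence in each of the two sections and a simple any-occurrence derivation, with no new data. Reported rates may come out slightly higher. Make the change before treatment codes are released for the final analysis.
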